PCT is a manualized evidenced-based PTSD treatment (Frost et al., 2014) used in several large-scale PTSD trials (e.g., Schnurr et al., 2007). It incorporates the essential therapeutic elements common to different types of psychotherapies, including supportive empathic listening and unconditional positive regard. The therapist plays an active role but does not impart any systematic training. The focus is to create an understanding of how the symptoms of PTSD are related to day-to-day difficulties and to help patients develop new, more adaptive responses to these stressors with a problem-focused and problem-solving approach. PCT includes weekly homework assignments. These include reading psychoeducational handouts and self-monitoring problems and stressors in a daily diary, which are then problem-solved in session. In prior trials, PCT showed equivalent change to active therapies at the last follow-up. The VA offers PCT as an evidence-based therapy for PTSD. So, this design element represents a conservative test of the superiority of AD-MIL.

Participants in both treatment arms will receive 12 weekly 90-minute sessions of individual psychotherapy.

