The therapist will query about adverse events (AEs) at every session by asking about any notable events since the last visit. These will be reviewed in a timely manner with the supervisor.

**Serious Adverse Event (SAE):** A SAE occurring in a patient or subject enrolled in a research study is serious if it results in any of the following outcomes: death, a life-threatening adverse drug experience, inpatient hospitalization or prolongation of existing hospitalization, a persistent or significant disability/incapacity, or is a congenital anomaly/birth defect. This will be reported to the IRB within 5 business days, as stated in reporting requirements. The only exception is death, which requires immediate reporting.

**Unanticipated Problems Involving Risk (UPR):** Defined as being (1) unexpected given the research procedures and characteristics of the population, (2) related (or possibly related) to participation in the research and (3) indicative that the research may place the subject or others at a greater risk of harm than was previously known. UPRs require notifying the IRB immediately.

Examples of possible UPRs for psychotherapeutic interventions:

1. Psychosis or mania
2. New onset or clinically significant exacerbation of a psychiatric disorder
3. Suicide and suicide attempts

An incident, experience, or outcome that meets UPR criteria generally will warrant consideration of substantive changes in the research protocol or informed consent process/document or other corrective actions in order to protect the safety, welfare, or rights of subjects or others. Examples of corrective actions or substantive changes that might need to be considered in response to an unanticipated problem include:

- \* modification of inclusion or exclusion criteria to mitigate the newly identified risks;
- \* implementation of additional procedures for monitoring subjects;
- \* suspension of enrollment of new subjects;

- \* suspension of research procedures in currently enrolled subjects;
- \* modification of informed consent documents to include a description of newly recognized risks; and
- \* provision of additional information about newly recognized risks to previously enrolled subjects.

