**PTSD Checklist for DSM-5 (PCL-5; Weathers et al., 2013b).** The PCL-5 will also be used to examine PTSD symptom burden. At the pre-eligibility screening, site RAs will ask veterans to write a one-sentence description of their worst and most currently distressing warzone experience on the top of the PTSD Checklist for DSM-5 (PCL-5) page and to rate symptoms referencing this event on the PCL-5. The PCL-5 will also be administered each week during therapy to track progress, capture adverse outcome, and model within-treatment change. The PCL-5 is similar to the PTSD Checklist (PCL) based on the DSM-IV. The PCL-IV has excellent psychometric characteristics (McDonald & Calhoun, 2010). The PCL-5 has 20-items which are scored in the past month on a scale from “0 = not at all” to “4 = extremely.”

Hypothesis B.5.

**Patient Health Questionnaire (PHQ-9).** This widely used and well-validated (Kroenke et al., 2001) measure will be used to measure depression. It has high internal consistency (e.g., Cameron et al., 2008) and correlates strongly with other measures of depression (Kroenke et al., 2001);

Hypothesis B.6.

**Trauma-Related Guilt Inventory (TRGI; Kubany et al., 1996).** The TRGI assesses guilty feelings and attitudes about a specific warzone event. It is scored into three scales (Global Guilt, Distress Scale, and Guilt Cognitions) and 3 subscales (Hindsight-Bias/Responsibility, Wrongdoing, and Lack of Justification).

**Trauma-Related Shame Inventory –Internal Shame Subscale (TRSI; Øktedalen et al., 2014).** The TRSI internal shame subscale is a 12-item self-report instrument designed to assess individuals' negative self-evaluations in the context of their traumatic experiences. The measure has good construct validity (Øktedalen et al., 2014).

Hypothesis B.7.

**The Schwartz Outcome Scale-10 (SOS-10; Blais et al., 1999).** Psychological health and distress will be measured using the SOS-10, a 10-item general mental health outcome measure. The SOS-10 has demonstrated good psychometric properties.

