### **ANALYSES**

**Inferential analyses.** The longitudinal and clustered nature of the design produces a multilevel or nested data structure (Raudenbush & Bryk, 2002), with a likelihood of between-subject variability in treatment trajectory over time (e.g. random slopes). In this study, veterans and therapists are nested (clustered) within performance sites. The lower level (level-1) data consists of the repeated measures for each individual at each assessment. Level-1 data is nested within upper level (level-2) person-level variables (e.g., study site).

Using the most up to date statistical software such as SAS 9.4 and R/R Studio, we will explore the change trajectory of endpoints over the course of pre-treatment, during-treatment, and post-treatment time intervals. Specifically, we will use the linear mixed model regression framework to assess the differential treatment effects of endpoint symptom burden over time. We will examine observed measurement scores and specify linear mixed models that best fit the time-change trends (e.g. linear, piecewise). We will test for the presence of random variation, such as between-site cluster effects and between-subject random slopes of treatment effect. We will determine the best fit linear mixed effects model as a combination of most appropriate representation of time and empirically-evidenced random and fixed effects.

The linear mixed effects models will incorporate clinically relevant time-invariant and time-varying predictors and will use Maximum Likelihood Estimation to produce estimates that are unbiased in the presence of random missingness and dropout. They will provide an Intent-To-Treat (ITT) analysis that will incorporate all available data. Per-protocol and “completer” subset analyses will be performed under the same paradigm. Additionally, a subset of subjects whom began therapy during the COVID-19 pandemic will be identified and analyzed separately; they comprise subjects which began therapy following December 31st, 2020. The tenability of the “At-Random” missingness assumption will be assessed and a sensitivity analysis of the results will be conducted to determine robustness of the inferences.

**Aim I:** Randomized controlled trial of AD-E, comparing it to PCT:

**Hypotheses 1 and 2:** Veterans in the AD-E arm will have a steeper downward slope in SDS (primary endpoint). Identical calculations will be performed with the B-IPF and DRRI-2 Post-Deployment Social Support measure.

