**Hypotheses 3-6:** Veterans in AD-E will have: (3) steeper downward PTSD symptom severity slopes (CAPS-5 and PCL-5) and lower incidence of PTSD cases (tested with Chi-square); (4) steeper slopes in depressive symptoms (PHQ-9); and (5) steeper slopes in shame and guilt (TRSI and TRGI); (6) steeper slopes in overall psychological distress (SOS) Separate models will be tested for each outcome. These models will be structured the same as the model used to test Hypotheses 1 and 2, with the above continuous measure scores designated as the outcome variables in separate analyses.

**Exploratory analyses:** Will AD-E be associated with steeper downward slopes in anger and aggressive behaviors (DAR-5, CTS2), suicidal ideation (DSI-SS), and alcohol abuse (QDS) as compared to PCT? Will AD-E be associated with steeper upward slopes in compassion towards self (SCS), compassion towards others (SBCS), and social connectedness (SoCS) as compared to PCT? The models used to evaluate these questions will be structured the same as the models above. We will be especially circumspect about statistically significant findings for these variables.

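### The weekly in-therapy PCL-5 carries a past-month recall period, so adjacent scores share about three-quarters of their window and early within-treatment change is smoothed and delayed

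*Combined protocol and SAP*

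**What the plan says.** The Measures section (B. Mental health change hypotheses) schedules the scale weekly and gives three uses for it: "The PCL-5 will also be administered each week during therapy to track progress, capture adverse outcome, and model within-treatment change." The same paragraph then describes the instrument: "The PCL-5 has 20-items which are scored in the past month on a scale from" 0 to 4. No section mentions a past-week version or a different instruction for the weekly sessions.

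The Treatment Arms section sets the length of the series: "Participants in both treatment arms will receive 12 weekly 90-minute sessions of individual psychotherapy." In ANALYSES the plan states: "we will explore the change trajectory of endpoints over the course of pre-treatment, during-treatment, and post-treatment time intervals." It leaves the form of the time trend to be chosen by fit. The PCL-5 is a named slope outcome there, with the AD arm expected to show "steeper downward PTSD symptom severity slopes (CAPS-5 and PCL-5").

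The adverse-event section adds a separate check: "The therapist will query about adverse events (AEs) at every session by asking about any notable events since the last visit."

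**The concern.** A month-long recall window sampled every week is a moving average. Each new score replaces about one week of recalled experience and keeps about three. At session 1 the window lies wholly before treatment, and it is still partly pre-treatment at sessions 2 to 4. That fits poorly with all three stated uses: following progress from week to week, picking up deterioration, and modelling change during therapy.

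The PCL-5 is the only symptom scale for which the documents describe a weekly schedule, so the during-treatment part of the trajectory appears to rest on it. At stake are the early slope, the location of any change point in a piecewise model, and how promptly a worsening appears in the score. The overlap also makes neighbouring scores correlated, and the ANALYSES section mentions site effects and random slopes but no residual serial correlation.

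**Working it through.** The plan gives no figure for recall overlap, so there is nothing to reproduce.

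**Inputs**
- Spacing: 7 days (Measures, PCL-5).
- Recall window W: one month (same paragraph). No day count is given, so W = 28, 30 and 31 days.
- Occasions: 12 weekly sessions (Treatment Arms). Assumption: one score per session, on days 0, 7, …, 77.
- Weighting of the month: not given. Assumed range: from even weighting to exponential recency weighting with a 7-day half-life over 30 days.

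**1. Overlap of successive windows** = (W − 7)/W: 21/28 = 75.0%, 23/30 = 76.7%, 24/31 = 77.4%. At two weeks, (W − 14)/W is 50–55%; at three weeks 25–32%; at four weeks 0–10%.

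**2. Share of a sudden change visible after k weeks.** Even weighting: 7k/W, capped at 1. Recency weighting with half-life h: (1 − 0.5^(7k/h)) / (1 − 0.5^(30/h)). For h = 7 and k = 1 this is 0.500/0.949 = 0.527.

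| Weeks after change | Even (W = 28–31) | Half-life 30 days | Half-life 7 days |
|---|---|---|---|
| 1 | 23–25% | 30% | 53% |
| 2 | 45–50% | 55% | 79% |
| 3 | 68–75% | 77% | 92% |
| 4 | 90–100% | 95% | 99% |

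**3. Slope over 12 sessions.** Let the true level be flat before session 1 and then change by one unit per day.

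- *Even weighting.* The score is t²/(2W) up to day W and t − W/2 afterwards. After a full window it runs parallel to the truth, W/2 (14 to 15.5 days) late. With W = 28, the scores on days 0, 7, 14 and 21 are 0, 0.875, 3.5 and 7.875, against −14, −7, 0 and 7 on the line t − 14. The excesses are 14, 7.875, 3.5 and 0.875. The least-squares slope changes by Σ excess × (t − 38.5) / Σ(t − 38.5)² = (−539.0 − 248.1 − 85.8 − 15.3)/7007 = −0.127, so the fitted slope is 0.873 of the true slope. With W = 30 it is 0.860, and with W = 31 it is 0.853.
- *7-day half-life, W = 30.* The mean age of the recalled day is about 8.5 days. The scores on days 0 to 28 are 0, 2.05, 6.77, 12.81 and 19.53. The excesses over t − 8.49 are 8.49, 3.54, 1.26, 0.30 and 0.02. The slope changes by −475/7007 = −0.068, giving 0.932.
- *First four weeks.* Observed change as a share of true change is 45–50% under even weighting (14/28 for W = 28) and 19.53/28 = 70% with the 7-day half-life.

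**4. Correlation from overlap.** If weekly states were independent and each score averaged four of them, adjacent scores would share three of four, a lag-1 correlation of 0.75.

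**5. With a past-week window.** Overlap is (7 − 7)/7 = 0 and a sudden change is fully visible at the next score (7/7). The only excess is 3.5 on day 0, so the slope changes by −3.5 × 38.5/7007 = −0.019, giving 98% of the true slope.

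**The case against.** The past-month statement sits in a general description of the instrument, and the weekly form itself is not in the documents. Sites may already use a past-week form. That stands as a limit on the premise: the mismatch is in the plan as written, not shown in practice. If a past-week form is in use, the plan should say so, because its scores would then have a different reference period from baseline and follow-up.

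A constant past-month window also has a merit. It keeps all PCL-5 scores on one metric across the pre-, during- and post-treatment trajectory. That is a real cost of changing, but a small one, because the session-1 weekly score can anchor a separate within-treatment model.

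Three stronger readings are tempting, and the documents do not support them:
- *That detection of worsening rests on the PCL-5.* It does not. Therapists ask about events since the last visit at every session and review them with the supervisor. The plan also sets no PCL-5 threshold for worsening, so no specified trigger is shown to be delayed. It remains true that the session query is not a symptom score.
- *That under a quarter of a sudden worsening is visible after a week.* That is the even-weighting extreme; recency weighting gives 30–53%.
- *That the within-treatment slope is badly flattened.* A steady trend is shifted, not flattened, once a full window has passed.

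Nor is the serial correlation pure artefact: the shared weeks carry real symptoms. What is artificial is that the same weeks are counted in several scores.

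**Conclusion.** The concern holds in a limited form. The overlap of 75–77% follows directly from the stated schedule and recall period for any length of month. The consequences are conditional. About 23–53% of a sudden change shows after one week, and the 12-session slope is about 85–93% of the true one. These figures assume weighting between even and a 7-day half-life; the slope figures also assume linear change that starts at session 1. The distortion falls mainly on the first four weeks and on turning points.

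A reader might infer that the trial's main result or the comparison of arms is biased. The documents do not support that. The recall instruction is the same in both arms, so it costs timing and precision without favouring either. The SDS primary endpoint, the CAPS-5 and the follow-up comparisons three months apart are untouched. This is a worthwhile low-cost improvement to the in-therapy PCL-5 series.

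**What to change.** - Use a past-week instruction for the weekly in-therapy PCL-5, and state it in the Measures section.
- Keep the past-month instruction at baseline and follow-up, and base the PCL-5 part of hypothesis B.4 on those scores.
- Fit the within-treatment trajectory to the weekly scores alone, anchored at the session-1 score, so that the two recall windows are not mixed in one slope.

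The cost is one changed line on the weekly form and about one sentence in ANALYSES. Weekly scores would no longer be interchangeable with baseline and follow-up scores, and any weekly points intended for the B.4 model would move to the separate one. A change made mid-trial needs a version indicator for weekly scores already collected.

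If the past-month form is kept for the weekly sessions, allow for serial correlation in the residuals of the within-treatment model, and do not interpret the timing of early change.

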### **C. Exploratory Hypotheses.**

**Dimensions of Anger Scale (DAR-5; Forbes et al., 2014).** Anger and aggression will be measured using the DAR-5, a 5-item measure of the frequency and intensity of anger in the past month. The DAR-5 has strong internal reliability and concurrent validity with the STAXI-2 (Forbes et al., 2014).

**Revised Conflict Tactics Scale; Physical Assault and Psychological Aggression subscales (CTS2; Straus & Douglas, 2004)** The CTS was designed to assess the use of reasoning, verbal aggression, and violence within the family (Straus, 1979), and over time has become the most widely used instrument to assess intimate aggressive behavior and violence (Straus & Douglas, 2004; Straus et al., 1996). The CTS2 poses 20 questions to assess five tactics used when there is conflict in the relationships of dating, cohabitating, or married couples (i.e., Assault, Psychological Aggression, Negotiation, Injury, and Sexual Coercion), and has been used to assess interpersonal conflict among friends, colleagues, and acquaintances, as well as within the family. Various versions of the CTS have been used in other studies of military personnel (Adler et al., 2008; Taft et al., 2007).

**Depressive Symptoms Index – Suicidality Subscale (DSI-SS; Metalsky & Joiner, 1997).** We will measure suicidal ideation with the DSI-SS which is a 4-item scale that focuses on ideation, plans, perceived control over ideation, and impulses for suicide. It is being used as a core measure in the Military Suicide Research Consortium. A review of measures of suicidal ideation and behaviors found that the DSI-SS had excellent internal consistency and concurrent validity (Batterham et al., 2014)

**Quick Drinking Screen (QDS; Sobell et al., 2003).** Alcohol use, alcohol abuse will be evaluated with the QDS which is a 4-item probe of frequency and quantity of alcohol consumption in the last month. The QDS has very good psychometric characteristics (Sobell et al., 2003).

**The Self Compassion Scale (SCS; Neff, 2003).** The 26-item Self-Compassion Scale includes 6 subscales (including Self-Kindness, Self-Judgment, Common Humanity, Isolation, Mindfulness, and Over-Identification) and measures overall self-compassion. The SCS has shown good internal consistency reliability as well as good test-retest reliability (Neff, 2003).

**The Santa Clara Brief Compassion Scale (SBSC; Hwang, Plante, & Lackey, 2008).** Compassion for humanity will be evaluated with the SBSC, a 5-item short form of the Compassionate Love Scale for Humanity (CLS). This scale has good reliability and is highly correlated with the original version (Hwang, Plante, & Lackey, 2008).

**The Social Connectedness Scale (SoCS; Lee and Robbins, 1995).** We will measure interpersonal closeness with the SCS, an 8-item scale that focuses on individual experiences in a social world (i.e., with peers, friends, and society) and the degree of difficulty in maintaining a sense of closeness. This

measure is being used as a core measure in the Military Suicide Research Consortium. The SCS has good psychometric properties (Lee and Robbins, 1995).

#### **D. Acceptability, tolerability, and feedback about AD-MIL.**

At the end of the study, we will ask veterans about their satisfaction with AD-MIL, the components that were most helpful, and the acceptability and tolerability of targeting military trauma with this treatment. We will incorporate the modal feedback into a final AD-MIL manual.

### **ANALYSES**

**Inferential analyses.** The longitudinal and clustered nature of the design produces a multilevel or nested data structure (Raudenbush & Bryk, 2002), with a likelihood of between-subject variability in treatment trajectory over time (e.g. random slopes). In this study, veterans and therapists are nested (clustered) within performance sites. The lower level (level-1) data consists of the repeated measures for each individual at each assessment. Level-1 data is nested within upper level (level-2) person-level variables (e.g., study site).

Using the most up to date statistical software such as SAS 9.4 and R/R Studio, we will explore the change trajectory of endpoints over the course of pre-treatment, during-treatment, and post-treatment time intervals. Specifically, we will use the linear mixed model regression framework to assess the differential treatment effects of endpoint symptom burden over time. We will examine observed measurement scores and specify linear mixed models that best fit the time-change trends (e.g. linear, piecewise). We will test for the presence of random variation, such as between-site cluster effects and between-subject random slopes of treatment effect. We will determine the best fit linear mixed effects model as a combination of most appropriate representation of time and empirically-evidenced random and fixed effects.

The linear mixed effects models will incorporate clinically relevant time-invariant and time-varying predictors and will use Maximum Likelihood Estimation to produce estimates that are unbiased in the presence of random missingness and dropout. They will provide an Intent-To-Treat (ITT) analysis that will incorporate all available data. Per-protocol and “completer” subset analyses will be performed under the same paradigm. Additionally, a subset of subjects whom began therapy during the COVID-19 pandemic will be identified and analyzed separately; they comprise subjects which began therapy following December 31st, 2020. The tenability of the “At-Random” missingness assumption will be assessed and a sensitivity analysis of the results will be conducted to determine robustness of the inferences.

**Aim I:** Randomized controlled trial of AD-E, comparing it to PCT:

**Hypotheses 1 and 2:** Veterans in the AD-E arm will have a steeper downward slope in SDS (primary endpoint). Identical calculations will be performed with the B-IPF and DRRI-2 Post-Deployment Social Support measure.

**Hypotheses 3-6:** Veterans in AD-E will have: (3) steeper downward PTSD symptom severity slopes (CAPS-5 and PCL-5) and lower incidence of PTSD cases (tested with Chi-square); (4) steeper slopes in depressive symptoms (PHQ-9); and (5) steeper slopes in shame and guilt (TRSI and TRGI); (6) steeper slopes in overall psychological distress (SOS) Separate models will be tested for each outcome. These models will be structured the same as the model used to test Hypotheses 1 and 2, with the above continuous measure scores designated as the outcome variables in separate analyses.

**Exploratory analyses:** Will AD-E be associated with steeper downward slopes in anger and aggressive behaviors (DAR-5, CTS2), suicidal ideation (DSI-SS), and alcohol abuse (QDS) as compared to PCT? Will AD-E be associated with steeper upward slopes in compassion towards self (SCS), compassion towards others (SBCS), and social connectedness (SoCS) as compared to PCT? The models used to evaluate these questions will be structured the same as the models above. We will be especially circumspect about statistically significant findings for these variables.

**Clinical significance:** Clinical significance will be calculated by the Jacobson-Truax (1991) method (e.g., Bauer, Lambert, & Neilson, 2004). This method suggests a two-step criterion. First, a reasonable cutoff between the dysfunctional and functional populations is established. Because normative data for veterans on the SDS does not yet exist, Jacobson and Truax's (1991) suggested cutoff A, defined as the point 2 *SDs* beyond the range of the pre-therapy mean (cutoff A =  $M_{clinical} - 2 SD_{clinical}$ ) will be used. Next, a reliable change index (RC) for each participant will be calculated to ensure that changes are not due to an artifact of measurement error. The RC is computed according to the following:  $RC = (x_2 - x_1)/S_{diff}$  where  $x_1$  represents the participant's pre-treatment SDS total score,  $x_2$  represents the participant's post-treatment or follow-up total score, and  $S_{diff}$  is the standard error of difference between the two test scores.  $S_{diff}$  will be calculated from the internal consistency of the measure at each time point. An RC larger than 1.96 reflects real change. Based on the two-step criterion, individuals will be classified as recovered (passed both cutoff A and RC criteria), improved (pass RC criterion but not cutoff A), unchanged (passed neither criteria), or deteriorated (passed RC criterion but symptom scores increased) for each follow-up interval. Chi-square analyses will be used to compare proportions per arm at each follow-up.

